1. Subject is willing to wear the Embrace watch on the wrist (alternatively ankle, if needed for younger children). Subjects are asked to wear the watch for as many hours of the day as possible, and for the entire night, if possible, for the 12-week duration of the sub-study.
2. Subject's parent/caregiver is willing to use the Alert App and receive voice and SMS notifications on their personal smart-phone, and ensure the smart-phone has internet connectivity; iOS 8.2 or higher is required for iPhone users.
3. Subject/subject's caregiver is willing to ensure that the Embrace watch remains within close proximity of the paired iPod Touch running the Empatica Alert app.

4. Subject/subject's caregiver is willing to ensure that the Embrace system is properly stored when not in use, and is not left exposed to direct sunlight, moisture, humidity or rain while in storage. The Embrace watch is water resistant but should never be submerged in water. Bathing and/or showering with the watch is acceptable, however.
5. Subject/subject's caregiver is willing to regularly clean the Embrace watch, routinely inspect the watch for sharp edges and damage, and ensure the watch is never worn over damaged or broken skin.
6. Subject/subject's caregiver is willing to ensure that the Embrace system is properly charged daily during a time when the subject is being observed so any seizures that occur during times that the device is not being worn are able to be added to the record manually.

**Exclusion Criteria:** Subjects meeting any of the exclusion criteria for main Study ZX008-1503 are not eligible for the sub-study. In addition, subject must not be enrolled into the sub-study if:

1. Subject has a known hypersensitivity to any of the Embrace device materials.
2. Subject has a clinically significant condition, or has had clinically relevant symptoms or a clinically significant illness in the 4 weeks prior to Visit 1, other than epilepsy, that would negatively impact study participation, collection of study data, or pose a risk to the subject.

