## **4.4 REMOVAL OF SUBJECTS FROM THERAPY OR ASSESSMENT**

While subjects are encouraged to complete all study evaluations, subjects may voluntarily withdraw from the sub-study for any reason at any time. Subjects who withdraw from the sub-study may still remain in the main study ZX008-1503. These subjects will then use only the ERT seizure diary. Subjects who are withdrawn from the main Study ZX008-1503 (either voluntarily or by the sponsor or investigator) must also be withdrawn from the sub-study. Subjects may be considered withdrawn or withdrawn by the investigator if they fail to return for visits, refuse to follow instructions regarding use of the Embrace watch or associated apps, lose or damage the Embrace in circumstances that do not support replacement, or become lost to follow-up for any other reason. All subjects who withdraw from the study early are required to return the Embrace watch and study iPod.

If premature withdrawal occurs for any reason, the investigator must make a genuine effort to determine the primary reason for a subject's premature withdrawal from the study and record this information on the case report form (CRF). All subjects who withdraw from the study with an ongoing adverse event (AE) must be followed until the event is resolved or deemed stable. If a subject withdraws prematurely after dosing, all data to be collected prior to discharge from the clinical site should be collected at the time of premature discontinuation or at the scheduled discharge.

For subjects who are lost to follow-up (i.e., those subjects whose status is unclear because they failed to appear for study visits without stating an intention to withdraw), the investigator should show "due diligence" by documenting in the source documents the steps taken to contact the subject (eg, dates of telephone calls, registered letters).

Subjects may withdraw their consent to participate in the study at any time without having to justify the reason for doing so. The decision to withdraw consent and discontinue participation in the study will not prejudice the subject's future medical treatment in any way.

In the event that the study is terminated prematurely then the procedure for termination should be followed as described in the main Study ZX008-1503 protocol. Concern for the interests of the subject will always prevail over the interests of the study.

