## **7. SAFETY INSTRUCTIONS AND GUIDANCE**

The Embrace is similar to other smartwatches that have been worn by patients over multiple days, and is believed to present minimal risk. The device passes a small current across the skin surface (similar to capacitive sensors in nature). It is non-invasive composed of well-established materials used in wearable devices and designed with ISO 10993-5 standards. The only notable risk so far has been that some wearers of similar devices occasionally develop contact dermatitis. Risk of contact dermatitis has been mitigated by restricting the use of common allergens – including nickel and cobalt, which affect 11.8% and 2.3% of the population, respectively (Mortz, et al 2013) – in the device materials and selecting grades of stainless steel that have nickel levels well below those required by EU REACH regulations. Occasionally skin reactions in similar devices may be caused by bacterial build-up on a watch or watch band as opposed to the material of the device itself so users will be reminded to clean the devices regularly.

To date, there have been two reports of allergic reaction related to wearing the Embrace watch.

**Subjects will be instructed to use the sensor only on the surface of healthy skin, to clean the sensor regularly, and to stop wearing it if the skin becomes red, itchy, or broken in any way.**

The Embrace system does not transmit radio signals that may interfere with hospital equipment or life-sustaining medical equipment. While the device has the capability of wireless transmission, it uses the Bluetooth standard, which is a reserved 2.4 GHz frequency band used in consumer electronics and within transmission power requirements. The device is compliant with IEC 60601-1-2:2014, EN 300 301 328 489 standards on electromagnetic emissions and interference. The rechargeable LiPol battery has an integrated protection circuit and the power system meets IEC 62133 standards.

Any unanticipated adverse device events (regardless of seriousness or severity) and unanticipated problems related to study participation should be reported as in the main Study ZX008-1503.

The physiological signals recorded using this device will not be used to make diagnostic or treatment decisions.

Safety monitoring will be done as per the main Study ZX008-1503 protocol.

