#### **8.4 STATISTICAL METHODS**

All safety data will be summarized as described in the main Study ZX008-1503 protocol and associated Statistical Analysis Plan. Efficacy analyses for sub-study participants that rely on the ERT seizure diary or are specific to the Embrace will not be included in the main Study ZX008-1503 analyses. Exploratory data for the Embrace watch system data will be processed as follows:

Continuous data will be summarized using descriptive statistics including means, standard deviations, medians, lower and upper quartiles, and ranges. Categorical variables will be summarized with frequencies and percentages. Confidence intervals will be calculated for key parameters or estimates as warranted.

A complete description of the statistical analyses and methods will be available in the Statistical Analysis Plan, which will be finalized before the database is locked.

The primary analysis will rely on descriptive statistics to summarize responses to the Ease of Use Questionnaire from each time point where the questionnaire is administered. In particular, the modal, ie, most frequent, response to each item on the questionnaire will be reported at each time point. Responses across all items on the questionnaire will be summed to create an overall index that will also be reported at each time point.

Exploratory data for the Embrace watch system data will be processed as follows:

- Embrace’s automated convulsive seizure detection results will be manually compared to the diary counts of convulsive seizures. Spearman rank correlation will be used to quantify agreement.
- The Spearman rank correlation described above will be repeated separately for events during periods of sleep and for events while awake, based on Embrace’s determination of sleep/wake (periods of sleep will be based on actigraphy and EDA as measured by the Embrace watch).

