## APPENDIX 1 – LIKERT EASE OF USE QUESTIONNAIRE

Over the last week, using the Embrace watch was:

- 1 – Very difficult
- 2 – Difficult
- 3 – Neutral
- 4 – Easy
- 5 – Very easy

Over the last week, using the Mate App was:

- 1 – Very difficult
- 2 – Difficult
- 3 – Neutral
- 4 – Easy
- 5 – Very easy

Over the last week, using the Alert App was:

- 1 – Very difficult
- 2 – Difficult
- 3 – Neutral
- 4 – Easy
- 5 – Very easy

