### APPENDIX 3 – SUMMARY OF CHANGES

Clarifications and changes were made to the protocol amendment 2.0, including removal of the Empatica Mate app (Empatica Mate Onboarding for iOS Devices) to collect and summarize seizure activity data, and inclusion of subjects who have successfully completed 14 weeks of treatment with ZX008 in Cohort 2 of study ZX008-1504. Parents/caregivers will use the ERT seizure diary to record the number/type of seizures.

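### The primary ease-of-use form has no answer for a week without use, so non-use cannot be told apart from a genuine rating

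*Combined protocol and SAP*

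**What the plan says.** - **Form.** Appendix 1 has three items, on the watch, the Mate App and the Alert App. All have a one-week recall ("Over the last week, using the Embrace watch was", "Over the last week, using the Mate App was", "Over the last week, using the Alert App was") and five options, from 1 (very difficult) to 5 (very easy). No option covers non-use.
- **Role and scoring.** The synopsis and Section 8.3.2 make change over time in this form the primary criterion. Section 8.4 reports the mode of each item at each time point, and adds: "Responses across all items on the questionnaire will be summed to create an overall index". It gives no rule for non-use or for a blank item.
- **Timing.** Table 1 places the form at Day 15, Days 30 and 60, and the end-of-study or early-termination visit (Day 90), where footnote c has the watch returned.
- **Foreseen non-use.** Section 7 instructs subjects "to stop wearing it if the skin becomes red, itchy, or broken in any way", without saying that they then leave the sub-study. Section 4.4 allows withdrawal of those who refuse to follow use instructions or who "lose or damage the Embrace in circumstances that do not support replacement". It has end-of-study procedures attempted at or near discontinuation, and treats data up to that point like those of completers.
- **Population.** Section 8.2.2 requires one week of valid Embrace seizure data, at any time in the extension.
- **Mate App.** Appendix 3 records "removal of the Empatica Mate app (Empatica Mate Onboarding for iOS Devices) to collect and summarize seizure activity data".
- **Wear period.** Synopsis inclusion criterion 1 asks for wear "for the 12-week duration of the sub-study". Section 3.1 also speaks of 12 consecutive weeks. Section 4.1 ties wear to the length of the sub-study and gives no number of weeks.

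**The concern.** The primary objective in Section 2.1 is usability, covering both correct use and ease of use. Stopping use is itself a usability result, and the form has nowhere to record it. A caregiver whose child did not wear the watch that week can pick a rating or leave the item blank. A middle rating from that caregiver looks the same as one from a caregiver whose child wore the watch throughout. The ambiguity falls mainly on people who stopped, whose experience a usability pilot most needs to understand. With at most 20 subjects, a few such answers can move the summary.

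**Working it through.** The plan has no power or precision figure to reproduce: the sample is up to 20 on grounds of feasibility (Section 8.1) and the primary analysis is descriptive.

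**1. Can a form fall due after a week without use?** Yes, by two routes.
- A subject stops wearing the watch for a skin reaction (Section 7) and stays in the sub-study. The next Table 1 form remains due.
- A subject is withdrawn under Section 4.4 and the form is due at early termination.

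Section 8.2.2 does not remove either form. A subject with one valid week early on and none later stays in the population.

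**2. Effect on the summed index.** Appendix 1 coding: three items scored 1 to 5, so the index runs from 3 to 15. (Section 3.1 gives the opposite direction, 1 for very easy and 5 for very difficult. That is a separate conflict to settle.) Assume 20 subjects, users answering 4 on every item (index 3 × 4 = 12), and k non-users who each answer s on all three items:

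mean index = [(20 − k) × 12 + k × 3s] / 20

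| k (assumed) | s = 1 | s = 3 | s = 5 | non-users excluded |
|---|---|---|---|---|
| 1 | 11.55 | 11.85 | 12.15 | 12 |
| 2 | 11.1 | 11.7 | 12.3 | 12 |
| 4 | 10.2 | 11.4 | 12.6 | 12 |

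For k = 2: (18 × 12 + 2 × 3)/20 = 222/20 = 11.1, and (18 × 12 + 2 × 15)/20 = 246/20 = 12.3.

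**3. How likely is at least one non-user?** The documents give no rate. If each of 20 subjects is independently a non-user in a given recall week with probability p, the chance is 1 − (1 − p)^20: 64% at p = 5%, 88% at 10% and 99% at 20%. All three rates are assumptions.

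**4. The Mate App item.** This needs no assumed rate, because the amendment removed the app for everyone. If a user answers 4 on the watch and 4 on the Alert App (sum 8), the Mate App answer takes the index to anything from 8 + 1 = 9 to 8 + 5 = 13 with no study use behind it. Without the item the index runs from 2 to 10.

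**5. The Day 90 form.** Twelve weeks are 12 × 7 = 84 days.
- If wear stops on Day 84, the seven days before the visit (Days 83–89) hold 2 wear days, or 1 if the visit day is counted (Days 84–90).
- If wear continues until the watch is returned on Day 90, the week is full.
- The weeks before Days 15, 30 and 60 are full on either reading. In the optional extension the end visit (Day 150) precedes 24 weeks (24 × 7 = Day 168), so no gap arises.

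**The case against.** Several points on the other side are sound.

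- **Day 90.** A reader might infer that every completer's last form covers mostly unworn days. The documents do not support that as a general statement. It requires wear to stop on Day 84, whereas Section 4.1 ties wear to the length of the sub-study, the synopsis calls participation approximately 12 weeks, and the watch is handed back only at the end visit. What remains is wording to reconcile.
- **Every withdrawal.** A reader might infer that all withdrawn subjects complete a form after use has stopped. Section 4.4 has the procedures done at or close to discontinuation, so a prompt form can still include wear days. Some subjects are lost to follow-up and complete none, refusing instructions is not the same as no use, and loss or damage may lead to replacement.
- **Worthless ratings.** A week of partial use still informs, and a caregiver whose child could not tolerate the watch may validly answer that it was difficult. The loss of meaning is confined to weeks with no use.
- **Blanks.** A reader might infer that a blank lowers the sum as if scored zero. No section says so.
- **Scale.** This is a descriptive pilot, so no test depends on the shift. A few forced answers among 20 may leave an item's mode unchanged. The one-valid-week rule already excludes subjects who barely used the watch.

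Section 8.4 also leaves the full methods to an analysis plan finalised before database lock, whose text is not in the documents. That plan can set a rule for blanks. It cannot recover a distinction that the form never collected. The withdrawal reason on the case report form does not show whether the recall week held any use, and it misses subjects who stop wearing the watch without withdrawing.

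**Conclusion.** The point holds for recall weeks with no use. The form cannot record non-use, the plan foresees it at scheduled and early-termination visits, and neither the scoring nor the analysis population separates the resulting ratings. The number affected is unknown. The range of 11.1 to 12.3 around 12 rests on 20 subjects, users at 4 on all three items, two non-users and the Appendix 1 coding, and it describes the mean index only. The Mate App defect is certain and affects the sum at every visit. The Day 90 shortfall is conditional on wear ending at Day 84 and is not part of the main conclusion. The change is worth making before the form is used further, because the lost information cannot be restored at analysis.

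**What to change.** 1. Add to each Appendix 1 item the answer *Not used in the last week*, with a reason (skin, refusal, lost or broken, technical, other). Report it as its own category at each time point and keep it out of the index.
2. At early termination, anchor the items to the last week in which the watch was worn.
3. Remove the Mate App item and state the new index range of 2 to 10.
4. State in Section 8.4 how the index is formed when an item is blank or marked as not used.
5. Separately, reconcile the 12 weeks of use in the synopsis and Section 3.1 with the Day 90 end visit and watch return in Table 1 and with the wear period in Section 4.1.

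The cost is one revision of a study-specific form, a few sentences in the protocol, and an index based on slightly fewer forms. Forms already completed on the present version would lack the new category and should be identified as such. If item 5 were met by moving the end visit, the stress, quality-of-life and anxiety and depression scales and the device return in the same Table 1 column would move too. Clarifying the wear period in the text avoids that.

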**Study Product, Dose, and Mode of Administration:**

ZX008: supplied as an oral solution in a concentration of 2.5 mg/mL. Subjects will be titrated to an effective dose beginning with 0.2 mg/kg/day (maximum: 30 mg/day). Study medication will be administered twice a day (BID) in equally divided doses with food.

Empatica Embrace watch system (Embrace)/Embrace Alert app: The noninvasive Embrace wrist-worn monitoring device, reads physiological data (EDA, skin temperature, and motion) from the surface of the skin and can transmit it wirelessly to a receiver. The watch is used in conjunction with the Embrace Alert app. The Alert app detects events from user physiology, such as convulsive seizures, and sends an alert to a caregiver via a phone call or text message. The Alert app runs on an iPod Touch and must remain in close proximity of the patient.

**Duration of Treatment:** Subjects will be permitted to participate in the sub-study for the initial 12 weeks of participation in the main OLE study (ZX008-1503). Subjects may have the opportunity to extend participation in the sub-study for up to 24 weeks.

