### 3. INVESTIGATIONAL PLAN

#### 3.1 OVERALL STUDY DESIGN AND PLAN

This is a sub-study to the ZX008-1503 OLE study. All participants in this sub-study will have participated in Study ZX008-1501 or ZX008-1504 Cohort 2 in the United States or Canada and then continued in Study ZX008-1503, which is a multicenter, open-label, long-term safety study of ZX008 (fenfluramine hydrochloride) in pediatric and young adult subjects with Dravet syndrome. The main Study ZX008-1503 consists of a 12-month OLE Treatment Period and a 2-week Post-Dosing Period in which all subjects will receive ZX008 starting at 0.2 mg/kg, titrating to an effective dose, up to 0.8 mg/kg/day (not to exceed 30 mg/day). Thus, subjects who complete the main study will have been treated with ZX008 for a minimum of up to 1 year. This sub-study will include up to 20 participants who meet the entry criteria for the main Study ZX008-1503 and who are willing to wear the Embrace watch and their parent/caregiver who is willing to use the Embrace Alert app per the user instructions for 12 consecutive weeks. Those invited to participate will undergo all procedures included in the main Study ZX008-1503, plus any additional procedures for the sub-study. At the conclusion of the sub-study, participants will only use the ERT seizure diary for the remainder of their participation in the main Study ZX008-1503. Efficacy analyses for sub-study participants that rely on the ERT seizure diary or that are specific to the Embrace watch will not be included in the main ZX008-1503 analyses.

At the time of consent for the main Study ZX008-1503 subjects will also be presented with the consent for this sub-study. Subjects who consent to participate in the sub-study will be fitted with an Embrace watch at Study Visit 1. Subjects (and/or parents/caregivers) will also be given instructions on how to use the Embrace system. The Alert app must be running on the provided iPod touch and remain in close proximity of the patient. However, parents/caregivers will continue to use the ERT seizure diary to record the number/type of seizures, use of rescue medication, and study drug administration.

At pre-determined assessment times, parents/caregivers will complete questionnaires specific for the sub-study, including:

1. Ease of Use Questionnaire, which comprises a 5-point Likert scale (1- Very easy, to 5- Very difficult).
2. Perceived Stress Scale (PSS), which consists of 10 items.

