#### **8.3.2 Efficacy Analysis**

The primary criteria for evaluation in the sub-study is the change over time in the 5-point Likert Ease of Use Questionnaire to measure user experience.

Secondary exploratory efficacy criteria for evaluation include change over time in the following:

- Perceived Stress Scale (PSS) to measure caregiver burden.
- Correlation of monthly (28-day) convulsive seizure count between the Embrace watch and seizure diary.
- Size of EDA response during and in the post-ictal hour of convulsive seizures.
- Skin-surface temperature (measured on wrist).
- Frequency of fever-related convulsive seizures.
- Comparison of convulsive seizure count during periods of sleep, and during the combined titration and maintenance periods between the Embrace watch and seizure diary.
- Correlation of convulsive seizure time and classification as determined by Embrace watch and seizure diary.
- EQ-5D-5L to measure quality of life of the parent/caregiver quality of life while using the Embrace.
- HADS to measure affective symptoms of the parent/caregiver while using the Embrace.

All other efficacy criteria are identical to those in the main Study ZX008-1503.

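### The summed ease-of-use index still includes an item on the Mate App, which the current study does not supply, so one third of the index does not measure the system in use

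*Combined protocol and SAP*

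**What the plan says.** Section 8.3.2 sets the primary measure: "The primary criteria for evaluation in the sub-study is the change over time in the 5-point Likert Ease of Use Questionnaire to measure user experience". Section 8.4 describes its analysis as descriptive, with two outputs. The first is item by item: "the modal, ie, most frequent, response to each item on the questionnaire will be reported at each time point". The second is a total: "Responses across all items on the questionnaire will be summed to create an overall index that will also be reported at each time point".

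Appendix 1 holds the questionnaire. It has three items, each rated from 1 (very difficult) to 5 (very easy):

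1. "Over the last week, using the Embrace watch was"
2. "Over the last week, using the Mate App was"
3. "Over the last week, using the Alert App was"

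The current text describes a different set of tools. On the device, the synopsis says: "The watch is used in conjunction with the Embrace Alert app". For seizure recording, Section 3.1 says that "parents/caregivers will continue to use the ERT seizure diary to record the number/type of seizures". Section 4.1 requires caregivers to be willing to use the Alert app and names no other app. Section 6.2.2 describes two software components, the Alert app and the MyEmbrace web portal, and says families need not see the portal.

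**The concern.** The second item asks for a rating of an app that caregivers are not given. The form has no not-applicable option, so a caregiver can only guess or skip. Section 8.4 then adds whatever results to two real ratings.

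This affects the measure the sub-study exists to report. The primary criterion is change over time, so what matters most is a shift between visits in how the Mate item is handled. If caregivers guess at Day 15 and later learn to skip it, the index falls although nothing about the watch or the Alert app has changed. With at most 20 subjects, a few such forms move the mean. The item-level output is also affected, because a most frequent response would be reported for an app that was not in use.

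**Working it through.** The plan states no index range, target value or power calculation, so there is no figure to reproduce. The check uses the item count and scoring in Appendix 1 and the summing rule in Section 8.4.

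**Share of the index.** For *k* items scored 1 to 5 and summed without weights, the range is *k* to 5*k* and the span is 4*k*.

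| | As written (*k* = 3) | Without the Mate item (*k* = 2) |
|---|---|---|
| Range | 3 to 15 | 2 to 10 |
| Span | 12 | 8 |
| Mate share of items | 1/3 = 33.3% | 0 |
| Mate share of maximum | 5/15 = 33.3% | 0 |
| Mate share of span | 4/12 = 33.3% | 0 |

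**One caregiver.** Take a caregiver who rates both the watch and the Alert app 4 (easy). The genuine information is 4 + 4 = 8 on a scale of 2 to 10.

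| Mate item | Three-item index |
|---|---|
| Answered 1 to 5 | 9 to 13 |
| Answered 3 | 4 + 3 + 4 = 11 |
| Answered 4 | 4 + 4 + 4 = 12 |
| Blank, answered items summed | 4 + 4 = 8 |
| Blank, prorated to three items | (8/2) × 3 = 12 |
| Blank, index set to missing | none |

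The plan does not choose among the last three rows. Summing the answered items is the literal reading of Section 8.4. Under it, 8 on the 3-to-15 scale averages 8/3 = 2.67 per item, which on the Appendix 1 anchors lies between difficult and neutral for a caregiver who found both tools easy.

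**Level at one visit (illustration).** Assume all caregivers rate both tools 4, half leave the Mate item blank, and blanks add nothing.

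- The others answer 3: mean = (11 + 8)/2 = 9.5, against 11 with no blanks.
- The others answer 4: mean = (12 + 8)/2 = 10, against 12 with no blanks.

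**Change over time (illustration).** Keep the true ratings at 4 and 4 throughout. Assume half the caregivers answer the Mate item 3 at Day 15 and none answer it later.

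- Day 15: 8 + 0.5 × 3 = 9.5
- Later: 8 + 0 = 8.0
- Apparent change: 8.0 − 9.5 = −1.5, with no change in usability.

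With 20 subjects, each caregiver who moves from answering 3 to leaving a blank shifts the mean by 3/20 = 0.15.

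**The case against.** The strongest counter-arguments concern size, not the contradiction itself.

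- **The index is only part of the primary analysis.** Section 8.4 gives the item-level modes first, and those for the watch and the Alert app are untouched. The study is an exploratory pilot sized on feasibility, and no test or decision depends on the index. This is true and limits the damage. The sum is still reported as part of the primary analysis and still cannot be interpreted as written.
- **Scoring a blank as nothing is an assumption.** Section 8.4 leaves full methods to a SAP to be finalized before database lock, which could prorate or set the index to missing. This stands, so the figures of 8, 9.5 and 10 are illustrations. A later scoring rule could deal with blanks, but it cannot give meaning to a guessed answer about an app that was not supplied.
- **A constant pattern cancels.** If the same caregivers skip the item at every visit, change over time is not distorted. That is correct: the trend is distorted only when skipping or guessing changes between visits, and nothing in the plan prevents that.
- **The direction is unsettled.** Section 3.1 anchors the scale the opposite way from Appendix 1, with 1 as very easy. Under that coding a blank makes the score look better instead of worse. The index is distorted either way, and the anchors need their own reconciliation.
- **Some families may have used the app.** The summary of changes in Appendix 3 shows that the Mate app belonged to the earlier design. The documents do not say whether anyone enrolled then. For such families the item would be valid, but their three-item totals would not be comparable with those of later participants.

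**Conclusion.** The concern holds. Appendix 1 and Section 8.4, read together, put into the primary summary an item about an app that the rest of the current protocol does not provide. The conflict lies within the current text. The summary of changes only suggests the cause: it records removal of the app but lists no edit to Appendix 1.

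The size by construction is one third of the items, of the maximum and of the span. That is not a claim about observed variance, which depends on the answers given. If every caregiver always skips the item, the index becomes in effect a two-item sum, and its scoring is left undefined. The apparent change of −1.5 points rests on the assumed answering pattern and on blanks adding nothing; it shows what the plan permits and is not a forecast.

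**What to change.** Delete the Mate App item from Appendix 1, and from the CRF if it appears there. In Section 8.4, define the index as the sum of the watch and Alert app items, with range 2 to 10, and report modes for those two items only. If forms with the Mate item have already been completed, leave that item out of the index at every time point and for every subject; this also keeps anyone who used the app under the earlier design comparable with the rest.

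Add a rule for a missing answer to either remaining item. Reconcile the scale anchors in Section 3.1 with those in Appendix 1 in the same amendment, so that the direction of the index is fixed.

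The cost is an appendix and CRF edit and a sentence or two in Section 8.4. The index range changes from 3–15 to 2–10. No visit, subject or extra data collection is needed.
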